5.1 Inclusion criteria

A subject will be eligible for inclusion in this trial if all of the following criteria apply:

- 1. Unilateral ISSNHL with onset within 72 hours prior to study treatment;
- 2. Mean hearing threshold of equal to or worse than (≥) 60 dB averaged across those 3 contiguous air conduction audiometric pure tone frequencies that show the highest mean hearing loss compared with the unaffected contralateral ear or, in case of history of asymmetric hearing, corresponding values from a pre-existing audiogram for the affected ear not older than 2 years prior to the ISSNHL incident (defined as "pure tone average", PTA)*;
- 3. Mean hearing loss of equal to or worse than (≥) 40 dB averaged across the air conduction thresholds at the pure tone average frequencies compared with the unaffected contralateral ear or, in case of history of asymmetric hearing, corresponding values from a pre-existing audiogram for the affected ear not older than two years prior to the ISSNHL incident*;
- 4. Age \geq 18 years on the day of screening;
- 5. Negative urine pregnancy test for women of childbearing potential. Women are not considered to be of childbearing potential if they meet one of the following criteria:
 - a. They have had a hysterectomy or tubal ligation at least one cycle prior to signing the Informed Consent Form (ICF) or
 - b. They are post-menopausal, with at least one year since their last menstrual period;
- 6. Willing and able to attend the trial visits;
- 7. Able to read and understand trial documents and follow Investigator and trial personnel instructions during visits, including audiology measurements;
- 8. Willing and able to use adequate hearing protection and to refrain from engaging in activities or work involving loud noise exposure where sufficient hearing protection is not possible or ensured for the duration of their participation in this study;
- 9. Willing and able to protect the ear canal and middle ear from water exposure for as long as the tympanic membrane is not fully closed;
- 10. Signed Institutional Review Board (IRB) / Independent Ethics Committee (IEC) approved ICF.
- * In subjects assessed within the first 24 hours from ISSNHL onset inclusion criteria 2 and 3 have to be confirmed by a second measure that is conducted, at the earliest, 24 hours after the onset of ISSNHL. This confirmatory assessment will serve as baseline value.

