9.4 Reporting

9.4.1 Trial specific rules for reporting

All AEs, including SAEs and clinically relevant abnormalities in laboratory test variables, will be monitored and documented from the time point of ICF sign off during TV until FUV4 (see Section 9.1).

The Investigator should ask the trial subject in a non-leading manner about the state of his/her health in order to elicit information on AEs which may have occurred since the last visit. Any clinically significant observations made during the visit itself also constitute AEs. The Investigator should make an assessment for AEs at each visit and record the events in the source documentation and in the CRF on the "Adverse Events" pages. Follow up information must be entered as soon as available.

Wherever possible, a specific disease or syndrome rather than individual associated signs and symptoms should be identified by the Investigator and recorded on the CRF. However, if an observed or reported sign, symptom or clinically significant laboratory abnormality is not considered a component of a specific disease or syndrome by the Investigator, it should be recorded as a separate AE in the source documents and on the CRF. Additionally, the condition that led to a medical or surgical procedure (e.g., surgery, endoscopy, tooth extraction, transfusion) should be recorded as an AE, not the procedure.

Any medical condition already present at the baseline medical assessment will be documented as medical history. If a medical condition or signs or symptoms present at baseline worsens (e.g. change in severity or seriousness) at any time during the trial, this should be reported as an AE.

SAEs will be followed until the event resolves or stabilizes or up to 2 months after FUV4. The Investigator is obliged to assist with the follow-up of SAEs. In case a SAE occurs after the subject has completed the trial and the Investigator considers this event related to the IMP or trial procedures, it should be reported immediately. The Investigator must contact the CRO Safety Manager to determine how the SAE should be documented and reported.

Any AE that is still ongoing after a subject's final visit will be recorded as ongoing in the CRF. However the Investigator will continue to follow up ongoing SAEs for the time frame described above and record information in the source documents and on the *Follow-Up SAE Form*.

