9.4.2 Reporting of SAE, pregnancy and pregnancy outcome by the Investigator

All SAEs, pregnancies, as well as pregnancy outcomes qualifying as serious must be reported to the CRO's Clinical Safety in an expedited manner, i.e. within 24 hours of awareness.

To report the SAE, the Investigator must complete the SAE form electronically in the electronic data capture (EDC) system for the study. When the form is completed, the CRO's Clinical Safety personnel will be notified electronically, will retrieve the information and will confirm receipt to the investigator by email. If the event meets seriousness criteria and it is not possible to access the eCRF, the Investigator must send an e-mail to the CRO's Clinical Safety or must send a fax of the completed paper SAE form within 24 hours of awareness.

These events (regardless of the causality assessment) should be reported in writing (fax transmission, electronic form or via e-mail) or orally. Oral reports must be followed up with a written report as soon as possible and documented in source notes with date and time of communication. In all cases, the Investigator or designee must submit a completed Report Form within 24 hours after the study site became first aware of the event.

The minimum information to report is:

- Subject ID;
- Study code;
- IMP kit number;
- Date and time of administration of IMP;
- Date and time of start of SAE;
- Description of SAE (AE reported term);
- Severity of SAE;
- Assessment of causality relationship (will follow a yes/no category);
- Name, contact details of person reporting the event.

A CRO team member will then review all documentation together with the Medical Monitor and follow up with the investigative site to obtain all the additionally required information.

The Investigator must continue to follow the subject until the SAE resolves or stabilizes or up to 2 months after FUV4.

Within 24 hours of receipt of follow-up information, the Investigator must update the SAE form electronically in the EDC system for the study and must submit any supporting documentation (e.g., blinded subject discharge summary or autopsy reports) via email or fax to CRO's Clinical Safety. If it is not possible to access the EDC system, refer to the procedures outlined above for initial reporting of SAEs.

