7.3 MISSING DATA

Complete missing or partial date will be presented in the listings as reported on CRFs. Missing or incomplete onset dates for adverse events and concomitant medications will be imputed as needed in order to determine treatment emergence or determine the prior and concomitant medications. The partial start date will be imputed as the first day of that month or year. The partial stop date will be imputed as the last day of that month or year.

Except the date imputation specified above, no missing data imputation will be applied to the descriptive analysis of efficacy and safety analysis of this study.

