In the summary subjects may be counted under multiple SOCs and PTs, but for each SOC and PT, subjects are counted only once. If a subject has the same TEAE on multiple occasions, the highest severity (severe, moderate, mild) recorded for the event will be presented and the highest drug relationship, reclassified into related and not related, will be presented on the respective tables. Missing severity is assumed to be severe, and missing relationships are assumed to have a definite relationship to the IMP or intratympanic IMP administration procedure. Percentages are based on the number of subjects in the safety population.

Listings will be provided for all AEs, AEs leading to discontinuation, and SAEs.

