11 INTERIM ANALYSES

[figure not shown]
Due to the study being terminated early, the interim analysis is not performed.

Page 40 of 65

Due to the early termination of the study, only 56 subjects are enrolled. The following are changes from the protocol:

- Only partial and missing dates of adverse events and medications are imputed to determine treatment emergence or determine the prior and concomitant medications. All other Imputation of missing values specified in the Protocol section 11.2 is not performed.
- Due to the small sample size, only descriptive analysis is performed in efficacy and safety endpoints.
- Interim analysis will not be performed and conditional power will not be calculated.
- Additional enrollment of subjects based on the results of interim analysis is no longer applicable.
- Tinnitus complete remission is considered given when the subject answers the question about tinnitus presence with "No"; it is not required that in addition both the Tinnitus Loudness Question (TLQ_{Loudest}) and Tinnitus Annoyance Question (TAQ_{Worst}) are rated as zero.
- Addition of analysis of efficacy outcomes by severity subgroup (profound / ≥ 90 dB PTA, severe / < 90 dB PTA at baseline).

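### SAP 7.3 imputes partial AE onset dates to the first of the month or year with no floor at the IMP date, so post-dose AEs dated only by the dosing month or year fall before Day 0

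*SAP*

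**What the plan says.** SAP 7.3 says that missing or incomplete AE onset dates "will be imputed as needed in order to determine treatment emergence". It then gives one rule for partial start dates: "The partial start date will be imputed as the first day of that month or year". Apart from these date rules it allows no imputation in the efficacy and safety analyses. The SAP's list of changes from the protocol repeats the purpose: "Only partial and missing dates of adverse events and medications are imputed to determine treatment emergence".

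SAP 7.2 defines study day as event date minus first dose date, with dosing as Day 0. SAP 10.1.2.1 defines a TEAE as an event that was absent before treatment, or that worsened relative to the pre-treatment state. For other missing AE attributes the same section takes the worst case: "Missing severity is assumed to be severe, and missing relationships are assumed to have a definite relationship".

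None of these places ties an imputed onset to the IMP date. SAP 7.3 covers missing as well as incomplete onsets, but gives no rule for a fully missing one. Part of Protocol 11.2 is blacked out. I rely on SAP 7.3, which states its date rule without reference to dosing.

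**The concern.** Imputing to the first of the period moves an onset date backwards. When that period contains the dosing date, the imputed onset falls before dosing even though the AE began afterwards. For AEs that truly began after dosing, the error can only run towards not emergent. The rules for missing severity and relationship lean the other way, so the SAP is cautious about how an event is graded but not about whether it is tabulated.

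All 12 planned AE summary tables (14.3.1.1 to 14.3.1.12) count TEAEs only. Protocol 2.5.2 reports that in earlier trials most local AEs occurred during or around IMP administration. Month-only dates are misplaced most often in that period.

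**Working it through.** The documents give no figure for this rule, so there is nothing to reproduce. I applied the rule literally.

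**Inputs**
- Imputed onset = first day of the known month or year (SAP 7.3).
- Study day = event date minus dose date, dosing = Day 0 (SAP 7.2).
- Follow-up to Day 91 (SAP 4).
- AE collection: AEs "will be monitored and documented from the time point of ICF sign off during TV until FUV4" (Protocol 9.4.1).
- 56 subjects enrolled; recruitment stopped on 28 November 2017 (SAP 4).
- Assumptions: dosing dates uniform over the calendar and onset days uniform over follow-up. The main run uses the 365 dates of 2017. The check uses the 607 dates from 1 April 2016 (assumed start; Protocol 4.3 says Q2 2016) to 28 November 2017.

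**Example.** Dose 15 May 2017, true onset 18 May 2017 (Day 3).
- Dated May 2017: imputed 1 May, which is Day -14.
- Dated 2017: imputed 1 January, which is Day -134.

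**Month-only dates.** For each onset day k, the share misplaced = (dosing dates for which the first of the onset month is before the dose date) / 365.

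| Onset day or range | Share misplaced |
|---|---|
| D0 | 0.967 |
| D7 | 0.737 |
| D14 | 0.507 |
| D28 | 0.049 |
| D30 | 0.000 |
| Mean D0-D28 | 0.507 |
| Mean D29-D91 | 0.0003 |
| Mean D0-D91 | 14.72 / 92 = 0.160 |

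The 607-date window gives 0.509 for D0-D28 and 0.161 for D0-D91.

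**Year-only dates.** The mean share over D0-D91 is 0.873 for the 2017 dates and 0.893 for the 607-date window. A start on 1 July 2016 gives 0.874. The range is about 87-89%.

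**With a floor at the IMP date.** None of the post-dose onsets is misplaced. The floor can instead count a pre-dose onset as emergent if it falls in the dosing month. The exposed interval is short: eligibility requires "Unilateral ISSNHL with onset within 72 hours prior to study treatment" (Protocol 5.1), and AEs are collected only from consent, so it is at most 3 days. For onsets on D-1, D-2 and D-3, the shares in the dosing month are 0.967, 0.934 and 0.901, a sum of 2.80 days. Over D-3 to D91 (95 days):
- current rule: 14.72 / 95 = 15.5% misclassified;
- with the floor: 2.80 / 95 = 3.0%, an upper figure because it assumes the full 3 days.

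**Weight of one event.** 56 / 3 = 18.7, so arms of 18 or 19 if allocation was even. If a subject's only TEAE is lost, that arm's incidence falls by 1/19 = 5.3 to 1/18 = 5.6 percentage points.

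**The case against.** The TEAE definition is substantive, not a date comparison. AEs are collected only from consent, and conditions present at baseline go to medical history (Protocol 9.4.1), so an AE entry is already evidence against a long pre-dose onset. In the example, Day -14 is earlier than any possible consent date. A programmer who noticed this could keep the event. This stands in part: loss from the tables is conditional on emergence being judged on the imputed date. But SAP 7.3 says that deciding emergence is what the date is for, and no fallback is written.

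Partial dates should also be rare. Visits at D3 and D7 follow dosing closely, CRF entries are fully verified against source (Protocol 14.2), and entries are checked for consistency (Protocol 14.5). The highest shares fall where dates are easiest to obtain, and later onsets, where recall may be poorer, have a share near zero for month-only dates. SAE reports require "Date and time of start of SAE" (Protocol 9.4.2), so mainly non-serious AEs are exposed; four of the 12 tables (14.3.1.4, 14.3.1.10, 14.3.1.11 and 14.3.1.12) cover only serious or fatal events. All of this stands and keeps the point small.

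A reader might infer that a displaced event also disappears from the listings, because Listing 16.2.7.1 is titled as treatment-emergent. The documents do not support that. SAP 10.1.2.1 says "Listings will be provided for all AEs, AEs leading to discontinuation, and SAEs", SAP 7.1 has all CRF data listed by subject, and SAP 7.3 shows partial dates as reported. The listing title is a labelling mismatch.

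**Conclusion.** The rule as written gives a wrong study day for a post-dose AE dated only by the dosing month or year, except when dosing was on the 1st or 1 January. If emergence is judged on that date, the event leaves the TEAE summary tables. SAP 7.3 also lacks a rule for a fully missing onset.

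The calculated shares are conditional on a partial date existing. They rest on uniform dosing and onset and on partial dating being unrelated to time since dosing; the documents give no data on any of these. The number of partial dates is unknown and may be zero.

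A reader might infer a biased comparison between arms or a threat to the safety conclusion. The documents do not support that either: the rule is the same in all arms, the analysis is descriptive only, and the primary safety endpoint is audiometric. The effect is limited to AE incidence counts. Minor.

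**What to change.** In SAP 7.3, for AE onset dates only, replace the partial start date rule with the following:
- If the known part of a partial onset date matches the month and year of IMP administration (or the year, when only the year is known), or if the onset is fully missing, impute the IMP administration date.
- Exception: if the recorded stop date is before dosing, class the AE as not treatment-emergent.
- In all other cases, impute the first day of the known month or year.

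Leave the medication rule unchanged. As an editorial correction, retitle Listing 16.2.7.1 to cover all AEs, in line with SAP 10.1.2.1.

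The cost is a few sentences, one programming change and one retitled listing. The downside is that a few partially dated events between consent and dosing, at most 3 days, may be counted as emergent. That error runs in the same direction as the SAP's worst-case rules for severity and relationship.

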7.4 VISIT WINDOWS

In general, all efficacy and safety data will be summarized by scheduled visits based on the scheduled events indicated in Table 1. The visits indicated on the eCRF (i.e., eCRF visit) will be used as the analysis visits for the efficacy and safety analysis.

The presence or absence of tinnitus and numerical rating scales for subjective tinnitus loudness "at its loudest" ($TLQ_{Loudest}$) and subjective tinnitus annoyance "at its worst" (TAQ_{Worst}) is collected at all visits from TV until FUV4. The data of tinnitus collected at all visits will be summarized by the scheduled visits.

In addition, a subject diary will be used for the subjects to self-record weekly the presence or absence of tinnitus and numerical rating scales. The data of tinnitus from the subject diary will be listed. Missing data are not imputed.

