5.3.2 Withdrawals

The Investigator should make all efforts to keep a subject in the trial.

Withdrawals are subjects who have been enrolled in the trial (i.e. ICF signed), but discontinue the trial after randomization. This may occur under the following circumstances:

- 1. The subject withdraws his/her informed consent to participate in the clinical trial. Subjects have the right to prematurely withdraw from the trial at any time and without any obligation to justify their decision;
- 2. The subject is lost to follow-up;
- 3. Subject's death;
- 4. The Investigator does not consider trial participation to be in the subject's best interest.

Any reasons for withdrawal after randomization must be documented carefully in the subject's medical records and in the case report form (CRF). If possible, the subject should attend a premature end of trial visit (see Section 7.4), which follows the course of assessments scheduled for FUV4.

A subject is considered lost to follow-up when the Investigator cannot reach the subject or, if contact details are available and permission has been obtained, the subject's relatives should be contacted by phone to obtain a reason for the subject not to attend a visit (e.g. an AE). If at least 6 phone calls or other contact efforts (e.g. e-mails, text messages) at different times of the day during a course of three weeks are not answered, a registered letter should be sent to the patient. All contact attempts should be documented in the patient's source documents. If the subject prefers to withdraw due to an AE, the Investigator should try to motivate the subject to continue until the event has stabilized with no further change expected, or the Investigator states the AE is not clinically significant and no further follow-up is required, but still encouraged. If the subject returns to the site at a later time point, the Sponsor should be informed to discuss further steps.

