7.4 End of the trial (regular or premature)

If the subject completes all visits as per the protocol, then FUV4 is the regular end-of-the-trial visit.

In case the subject terminates the trial prematurely, for whatever reason, an unscheduled end-of-the-trial visit should be performed at the earliest convenience. This visit follows the same procedures as visit FUV4 (refer to Section 7.2). In case termination occurs before FUV1, blood samples for laboratory assessments as foreseen for FUV1 are to be taken.

8 Study medication and concomitant medication

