4.1.1 Inclusion Criteria

A subject will be eligible for inclusion in this trial if all of the following criteria apply:

² Or premature end of trial visit in case the subject terminates the trial prematurely.

³ Only to be performed if tinnitus is present.

⁴ Only to be performed if eardrum is fully closed.

Session 5 Assessment to be repeated, at the earliest, 24 hours from onset if subject presenting within the first 24 hours from ISSNHL onset. If eligibility is confirmed, this second assessment serves as baseline measure.

⁶ If WRS (WRS_(80dB) and WRS_(60 dB)) and PTA assessments were done within 2 hours prior to subject inclusion (signing the informed consent form (ICF)) and within 5 hours prior to IMP administration, these assessments will be used as baseline values and therefore do not need to be repeated.

values and therefore do not need to be repeated.

Only to be done if subject receives background therapy. The background therapy documentation card is to be collected at FUV3.

- 1. Unilateral ISSNHL with onset within 72 hours prior to study treatment;
- 2. Mean hearing threshold of equal to or worse than (≥) 60 dB averaged across those 3 contiguous air conduction audiometric pure tone frequencies that show the highest mean hearing loss compared with the unaffected contralateral ear or, in case of history of asymmetric hearing, corresponding values from a pre-existing audiogram for the affected ear not older than 2 years prior to the ISSNHL incident (defined as "pure tone average", PTA)*;
- 3. Mean hearing loss of equal to or worse than (≥) 40 dB averaged across the air conduction thresholds at the pure tone average frequencies compared with the unaffected contralateral ear or, in case of history of asymmetric hearing, corresponding values from a pre-existing audiogram for the affected ear not older than two years prior to the ISSNHL incident*;
- 4. Age \geq 18 years on the day of screening;
- 5. Negative urine pregnancy test for women of childbearing potential. Women are not considered to be of childbearing potential if they meet one of the following criteria:
 - a. They have had a hysterectomy or tubal ligation at least one cycle prior to signing the Informed Consent Form (ICF) or
 - b. They are post-menopausal, with at least one year since their last menstrual period.
- 6. Willing and able to attend the trial visits;

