7 GENERAL ASPECTS FOR STATISTICAL ANALYSIS

7.1 GENERAL METHODS

The data analyses will be conducted using
Unless otherwise specified, all continuous efficacy and safety data will be summarized descriptively by treatment group and time point including changes from baseline (n, arithmetic mean, standard deviation, minimum, 25%-quantiles (Q25), median, 75%-quantiles (Q75) and maximum).
The stratification of initial PTA frequency range will be conducted on the 3 contiguous air conduction audiometric pure tone frequencies at TV. The 0.25 - 1 kHz, 0.5 - 2 kHz and 1 - 3 kHz will be defined as ≤ 2 kHz. The 2 - 4 kHz, 3 - 6 kHz, and 4 - 8 kHz will be defined as > 2 kHz.
Categorical variables will be summarized with frequencies and percentages by treatment group and time point.

For categorical variables, the number and percentage of subjects in each category will be summarized. Percentages will be displayed to one decimal place, except 100%, which will not show any decimals. Counts of zero will not have percentage displayed in order to draw attention to non-zero counts. Ratios will be displayed to 2 decimal places.

Unless otherwise specified, all efficacy and safety data summarized will include scheduled visits.

All data collected on CRFs and clinical database will be presented in by-subject listings for randomized set unless specified otherwise

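### SAP 7.4 puts no day limit on eCRF visits, so a premature end-of-trial result may be summarised as the Day 91 (FUV4) outcome

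*SAP*

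**What the plan says.** - **Visit assignment.** SAP 7.4 says that efficacy and safety data "will be summarized by scheduled visits based on the scheduled events indicated in Table 1", and then: "The visits indicated on the eCRF (i.e., eCRF visit) will be used as the analysis visits for the efficacy and safety analysis". The section is titled Visit Windows but gives no day limits and does not mention premature visits.
- **Table 1.** In both the SAP and the protocol, footnote 2 to the FUV4 column reads: "Or premature end of trial visit in case the subject terminates the trial prematurely".
- **Content of the premature visit.** Protocol 5.3.2 describes a visit "which follows the course of assessments scheduled for FUV4".
- **Timing of the premature visit.** Protocol 7.4 says "an unscheduled end-of-the-trial visit should be performed at the earliest convenience". It foresees that this may happen very early: "In case termination occurs before FUV1, blood samples for laboratory assessments as foreseen for FUV1 are to be taken".
- **Which visits are tabulated.** SAP 7.1 says that, unless otherwise specified, "all efficacy and safety data summarized will include scheduled visits".
- **Missing data.** Apart from dates of adverse events and medications, SAP 7.3 says "no missing data imputation will be applied to the descriptive analysis of efficacy and safety analysis of this study".

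**The concern.** Read together, these sections lead most naturally to the premature visit being labelled FUV4. With no day limit, a value taken days or weeks after treatment would then sit in the Day 91 row. Protocol 2.1 describes hearing as often recovering, partly or fully, over the days and weeks after onset, so an early value is not a Day 91 outcome.

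The rows affected are the important ones. FUV4 is the time point of the primary endpoint (PTA improvement), the main secondary endpoint (WRS at 80 dB) and tinnitus remission. It is also a time point of planned frequency tables such as the one for PTA improvement below 15 dB (SAP section 16, Table 14.2.3.6.1).

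There is a weaker, secondary point. Protocol 7.4 calls the same visit unscheduled, and SAP 7.1 speaks of scheduled visits. Under a different eCRF label, a value that falls inside a visit window might be listed but not tabulated. That would touch the FUV1 to FUV3 rows, including FUV3, the time point of the primary safety endpoint.

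**Working it through.** The plan gives no figure to reproduce. The check has two parts: which days are exposed, and how much one subject weighs.

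**1. Exposed days.** The audiometry windows follow from Table 1 (SAP and protocol):
- FUV1: D3 ± 1 = Days 2–4 (3 days)
- FUV2: D7 ± 2 = Days 5–9 (5 days)
- FUV3: D28 ± 5 = Days 23–33 (11 days)
- FUV4: D91 ± 7 = Days 84–98

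Before the FUV4 window opens there are Days 1–83. Of these, 3 + 5 + 11 = 19 lie in an earlier window and 83 − 19 = 64 lie in none. With an FUV4 label, a premature visit on any of the 83 days could appear as Day 91. With an unscheduled label, a visit on one of the 19 in-window days could drop out of the FUV1 to FUV3 rows.

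**2. Weight of one early leaver.** Inputs: 56 subjects enrolled and 1:1:1 allocation (SAP section 4). Assumption: all 56 were randomised and contribute, so n = 56/3 = 18.67 per arm. A second assumption, n = 14, shows the effect of fewer contributors.

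Counting the leaver's value x as FUV4, instead of leaving it out, changes the arm mean by

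mean(all) − mean(rest) = (x − mean(rest)) / n.

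The difference x − mean(rest) is not in the documents; 10, 20 and 30 dB are assumed.

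| Assumed difference | n = 18.67 | n = 14 |
|---|---|---|
| 10 dB | 0.54 dB | 0.71 dB |
| 20 dB | 1.07 dB | 1.43 dB |
| 30 dB | 1.61 dB | 2.14 dB |

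Protocol 10.1.1 calls 10 dB clinically relevant. Against that, the shifts are 5–16% (n = 18.67) or 7–21% (n = 14).

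In a frequency table one subject has weight 1/n: 1/18.67 = 5.4 percentage points, or 1/14 = 7.1. Tinnitus remission counts only subjects with ISSNHL-related tinnitus at baseline, so its denominator may be smaller and the weight larger.

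With no early leaver, every figure is zero.

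**3. Do other provisions remove such a value?**
- The Efficacy Analysis Set needs only one valid post-treatment PTA (SAP 6.2), so an early leaver can be in it.
- The reduced expert review in SAP 6.2 covers subjects with baseline PTA of 90 dB or more. Its listed criteria concern masking and recording, not study day.
- Time-window deviations may be discussed at the Blind Data Review Meeting, but for the Per Protocol set (SAP 6.3). The tinnitus and PTA-frequency tables are planned only on the Efficacy Analysis Set.

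None of these takes an early value out of the FUV4 row of the Efficacy Analysis Set tables.

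**The case against.** **The plan is not silent.** A reader might infer that the SAP has no rule at all for these visits. That goes too far: SAP 7.4 points to Table 1, and Table 1 ties the premature visit to the FUV4 column. What stands is narrower. This link is a note in a schedule of assessments, it is not stated as an analysis rule, and it has no day limit.

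**No breach of the no-imputation rule.** A reader might infer that putting an early value in the Day 91 row contradicts SAP 7.3. It does not. The value was observed at the subject's final visit, and tabulating it is a choice of visit label. The result resembles a value carried forward, but nothing missing has been filled in.

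**The unscheduled label is the weaker reading.** In Protocol 7.4 the word describes how the visit is arranged and is not an eCRF label. SAP 7.1 says which visits the summaries include and does not expressly exclude others. This is why it is only a secondary point.

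**The harm is doubly conditional.** It needs both an FUV4 label and at least one early leaver, and the documents give neither. They do not show that any FUV4 figure is in fact affected.

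**Tracing is possible.** All CRF data are listed by subject, study day is defined, out-of-window visits are a deviation category, and disposition shows early discontinuations. PTA and WRS at 80 dB also have Per Protocol summaries. This lowers the priority, but it does not change what the Efficacy Analysis Set tables would show.

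**Leaving early leavers out can also mislead.** This is correct. The figures above compare two ways of handling the value; they do not measure error against true Day 91 hearing.

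**Conclusion.** The point holds as an unstated and unbounded mapping. On the more natural reading of Table 1, following SAP 7.4 as written can label an early PTA, WRS or tinnitus value as the Day 91 outcome. The size is modest: 0.5 to 1.6 dB in an arm mean and 5.4 percentage points in a frequency, for one early leaver. This rests on the assumed 10–30 dB difference, on all 56 subjects contributing, and on an FUV4 label in the eCRF. Possible omission of in-window values from the FUV1 to FUV3 rows is secondary.

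The analysis is descriptive only (SAP 2.2), so no test or decision depends on it. Priority is minor: a cheap improvement.

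**What to change.** Keep the eCRF visit as the analysis visit for regular visits. Add to SAP 7.4, for audiometry, WRS and tinnitus values from a premature end-of-trial visit:

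1. Study day is counted from TV as Day 0 in all arms. (SAP 7.2 defines the first dose date only for subjects randomised to AM-111.)
2. The value counts as FUV4 only if taken on Days 84–98.
3. Otherwise it goes to the Table 1 window it falls in (Days 2–4, 5–9 or 23–33), provided the measure is scheduled there and no regular value exists.
4. All remaining values go in a separate row for premature end of trial, with study day shown. Examples are a Day 31 premature value after a regular Day 28 FUV3, or WRS at 60 dB, which is scheduled only at TV and FUV4.
5. Early-termination laboratory samples stay as Protocol 7.4 provides, that is, as those foreseen for FUV1.

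**Cost.** A few sentences and one mapping step for premature visits. The FUV4 n may fall slightly, and the FUV4 summary becomes observed-case, which can itself be selective. The separate row and an optional summary of the last available PTA offset this. One unevenness remains: a regular FUV4 held on Day 80 stays in the FUV4 row, with the deviation listing showing it, while a premature visit on Day 80 goes to the separate row.
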